1.5 Rationale for Focus on Metastatic Castrate-Resistant Prostate Cancer (MCRPC)

Our overarching objective is to determine the effect of exercise on overall survival among men with advanced prostate cancer. We have chosen to restrict our study population to men with progressive MCRPC because: 1) Men with progressive MCRPC are at high risk for death within a time frame that can be feasibly tested in the setting of a RCT (median OS on treatment = 32⁴² to 35⁴³ months). 2) With the proper use of stratification variables (treatment and study site), it is possible to define a homogenous study population in terms of risk of death; 3) This is the largest group of patients that can be uniformly considered to have advanced prostate cancer and thus provides the largest patient pool for recruitment while also meeting criteria 1 & 2; 4) while new therapies for MCRPC extend life,^{44,45} they also cause significant harm to metabolic and cardiac function and health-related QOL which may be attenuated or avoided through exercise; and 5) we hypothesize that exercise will have the largest measurable effect on OS among men with documented evidence of progressing MCRPC (in contrast to men with stable M1 CRPC, non-castrate resistant disease, or non-metastatic disease).

1.6 Rationale for Overall Survival (OS) as the Primary Endpoint

[figure not shown]
The primary endpoint for this randomised controlled trial will be overall survival (OS). OS was chosen as the primary endpoint because it has clear biological, clinical and public health significance and is a validated endpoint for approval of new treatments among men with MCRPC. Additionally, OS data can be obtained with minimal loss to follow-up through review of medical and death records. The median OS among men with MCRPC is 32⁴² to 35⁴³ months. Thus, OS is a feasible outcome to examine within the budget and timeline of the proposed study.

1.7 Study Design

There is compelling biological and clinical rationale for including exercise in the clinical management of men with MCRPC. We propose that psychosocial support plus exercise will increase OS compared to psychosocial support alone. This will be a phase III RCT of high intensity aerobic and resistance exercise training among men with MCRPC. The first twelve cycles (1 cycle=28 days) of training will be done under supervision which will include a structured period of tapered supervision to self-managed exercise; the training program will be self-maintained with text messages and in-person sessions to support self-maintenance for an additional 12 cycles.

Figure 2. Study Design

1 cycle=28 days

2.0 OBJECTIVES

Primary Objective:

- 2.1** To determine if high intensity aerobic and resistance training plus psychosocial support increases overall survival compared to psychosocial support alone in patients with metastatic castrate-resistant prostate cancer.

Secondary Objectives:

- 2.2** To compare progression free survival between the intervention and control groups.
- 2.3** To compare the time to first occurrence of a symptomatic skeletal-related event between the intervention and control groups.
- 2.4** To compare time to progression of pain, degree of pain, and opiate use between the intervention and control groups.
- 2.5** To compare change in levels of inflammation, energy metabolism, and androgen metabolism biomarkers between the intervention and control groups over time.
- 2.6** To determine whether biomarkers of inflammation, energy metabolism, and androgen metabolism are associated with overall survival and explore the extent to which these biomarkers mediate the hypothesized association between exercise and overall survival.
- 2.7** To compare physical and emotional quality of life between the intervention and control groups

3.0 ELIGIBILITY CRITERIA

3.1 Inclusion Criteria

- Patients must be mCRPC. This is defined as adenocarcinoma of the prostate with systemic metastatic disease despite castrate levels of testosterone (<50 ng/dL) due to orchiectomy or LHRH agonist.
 - Patients must have one or more of the following to be considered mCRPC
 - Metastatic Disease Progression: >20% increase in the sum of diameters of measurable lesions from the time of maximal regression or appearance of one or more new lesions.
 - Bone Scan Progression: Appearance of one or more new lesions on bone scan attributable to prostate cancer.
 - PSA Progression: PSA \geq 2 ng/ml that has risen serially on at least two occasions, each at least one week apart (PSA1 < PSA2 < PSA3).
- Castrate levels of testosterone must be maintained while on study. Be on androgen deprivation therapy (ADT) with a GnRH agonist/antagonist or prior bilateral orchiectomy. All patients will be required to be on ADT during the study period or have had a prior bilateral orchiectomy. Men with small cell neuroendocrine tumours or features of small cell disease are not eligible.
- At enrolment, patients must fit into one of the following 4 categories:
 1. Treatment naïve for mCRPC (have not yet started approved therapies for CRPC ie: Abiraterone/Enzalutamide/Apalutamide/Docetaxel; less than 4 weeks on approved therapies is still considered to be treatment naïve)

Or

 2. Receiving Abi/Enza/Apa for mCRPC AND responding or stable (PSA values must be stable or declining after at least 4 weeks since starting Abi/Enza/Apa for mCRPC)

Or

 3. Patients with PSA progression while on Abi/Enza/Apa are eligible as long as they are asymptomatic AND there is no intent on starting chemotherapy within 6 months

Or

 4. Patients treated with Docetaxel as first line therapy for mCRPC who are asymptomatic without ANY evidence of progression

Or

 5. Patients may have progressed following Docetaxel first line and are now receiving treatment with Abi/Enza/Apa. These patients must absolutely be responding or stable (PSA values must be stable or declining after starting Abi/Enza/Apa treatment) and have an expected life expectancy of more than 1 year.
- \geq 4 weeks since any major surgery and fully recovered.
- Halabi Nomogram score <195¹ (Risk Category rated as low or intermediate risk)
- Age \geq 18 years
- Eastern Cooperative Oncology Group (ECOG) performance status 0-1
- Patients must be able to travel to one of the study-designated exercise facilities up to three days per week for four weeks during cycle 0, two days per week for cycles 1-8 (32 weeks) and once per week for cycles 9-11 (12 weeks). In addition, patients must be able to attend exercise testing visits as outlined in the [Table 1](#).
- Required Initial Laboratory Values:
 - Absolute neutrophil count (ANC) \geq 1500/uL
 - Platelet count \geq 100,000/uL
 - Creatinine \leq 1.5 x upper limits of normal
 - Bilirubin \leq 1.5 x upper limits of normal
 - Aspartate aminotransferase (AST) \leq 1.5 x upper limits of normal
 - Serum testosterone \leq 50 ng/dL

- Medical clearance to undergo a symptom-limited cardiopulmonary exercise test (CPET) and vigorous aerobic and resistance exercise training.
 - [Appendix 8](#): Certain medical questions with 'YES' responses require cardiologist clearance or physician clearance to participate. See SOM for details.
- Successfully pass the screening CPET by achieving:
 - Volitional exhaustion (RPE \geq 9 using the Borg 0-10 RPE scale) in the absence of any cardiorespiratory abnormalities.
 - If cardiorespiratory abnormalities are identified, please refer the patient to his managing physician for further assessment and diagnosis.

Note: To assist practitioners with delivering valid CPET assessments, patients nearing exhaustion should achieve a respiratory exchange ratio (RER) of \geq 1.1.
RER is not a criteria of the test. This objective measure should only be used to assist practitioners with patient management and decision-making.
- Exercise Coordination Centre (ECC) review and approval of subject's screening bone scan/ areas with bone metastases.
- Subject is willing and able to use the technological aspects of the trial.
- The subject is fluent in the language as designated by the institution at which he would be enrolled.

3.2 Exclusion Criteria

- Previous radiographic or clinical progression (PSA progression is permitted) while on treatment with abiraterone, enzalutamide, apalutamide, or a combination.
- Previously identified small cell neuroendocrine tumours or pure small cell carcinoma of the prostate, based on a prior biopsy of the prostate.
- Brain metastases (brain imaging is not required)
- Previous and/or concurrent treatment with other anti-cancer treatments is permitted. Patients are allowed to be treated with chemotherapy during the duration of the trial. Patients who have received chemotherapy as part of initial androgen deprivation therapy for metastatic castration sensitive disease are eligible.
- Currently receiving experimental treatment with non-approved drugs at the time of enrolment. Patients must undergo a 28-day washout between last dose and screening CPET.
- Poorly controlled hypertension. During screening \geq 2/3 of readings must be $<$ 160/90, regardless of whether on a regimen of anti-hypertensive therapy or not.
 - If patient is currently taking hypertensive medication(s)/therapy, please indicate medication and include in the Treatment and Concomitant Medications Log (SOM: [Appendix 11](#)).
- Current congestive heart failure (New York Heart Association Class II, III or IV)
- Recent serious cardiovascular events (within 12 months) including, but not limited to, transient ischemic attack (TIA), cerebrovascular accident (CVA), or myocardial infarction (MI).
- Medical condition such as uncontrolled infection or cardiac disease that, in the opinion of the physician, would make this protocol unreasonably hazardous for the patient.
- Patients with a currently active second malignancy other than non-melanoma skin cancer. Patients are not considered to have a currently active malignancy if they have completed necessary therapy and are considered by their physician to be at $<$ 30% risk of relapse at time of assessment.
- Psychiatric illness, which would prevent the patient from giving informed consent or adhering to the study protocol.
- Serious or non-healing wound, ulcer, or bone fracture.
- Known spinal cord compromise or instrumentation due to metastatic disease in the mCRPC state. Radiation therapy for metastatic disease is allowed.
- Peripheral neuropathy \geq grade 3.
- Men participating in vigorous aerobic exercise for more than 60 minutes per week or structured

resistance exercise two or more days per week (seek ECC approval before exclusion).

- Experiences shortness of breath, chest discomfort, or palpitations when performing activities of daily living (patient with these symptoms can participate in the study with cardiologist clearance)
- Ongoing restriction of physical activity with physician documentation
- Has chest pain brought on by physical activity (patient can participate in the study with cardiologist clearance)
- Has developed chest pain in the past month (patient can participate in the study with cardiologist clearance)
- Moderate-to-severe bone pain (i.e., National Cancer Institute's Common Terminology Criteria for Adverse Events grade 2-3 bone pain).
- Men who do not complete the baseline lifestyle and quality-of-life questionnaires and 3-days of diet diaries or country-specific FFQ will not be eligible

4.0 SCREENING, RANDOMISATION, STRATIFICATION, BLINDING

4.1 Informed Consent

All patients must willingly consent after being informed of the procedures to be followed, the experimental nature of the intervention, alternatives, potential benefits, side effects, risks, and discomforts. Human protection committee approval of this protocol and its consent form are required. Informed consent is required before any study-specific procedure is performed. Patients who sign the study consent form should be entered into the screening database.

4.2 Screening

Patients who are potentially eligible for GAP4 and sign the study Informed Consent should be given a site specific screening ID, and entered into the database. Participants will continue to be screened for the trial until 866 participants have been randomised.

4.3 Enrolment

A physician must determine whether a patient is eligible for GAP4 based on the inclusion criteria. The screening CPET must occur within 14 days of Day 1, Cycle 0 (Baseline). Prior to randomisation, approved GAP4 institutions must have Site Coordination Centre (SCC) approval and enter all of the following information into the following online database forms:

Consenting

Subject Identification

Patient-completed Demographics, Exercise Screening, and Questionnaires Parts 1-4

Physician Clearance Form

Eligibility for CONSORT Reporting and Signed Eligibility Criteria Checklist

When the patient successfully completes screening procedures and is eligible for enrolment, a patient identification number (separate from the patient screening ID) will be assigned. Participants will continue to be enrolled onto the trial until 866 participants have been randomised.

4.4 Randomisation

After SCC approval, patients will be randomised in a 1:1 ratio to intervention (Supervised Exercise/SE) group or control (Self-directed Exercise/SDE) group, stratifying by treatment status at time of randomisation and study site. Randomisation will be performed through the study database but maintaining concealment from patients and recruiting staff, upon which time a Study ID will be assigned to the subject.

4.5 Stratification

Patients will be stratified by study site and treatment status at the time of registration: 1) Patients who are treatment naïve or stable on Abiraterone/Enzalutamide/Apalutamide or 2) Patients who are on/received first line chemo OR progressing on first line Abiraterone/Enzalutamide/Apalutamide. Patients treated with radium-223 will need medical monitoring review for correct stratification placement. Previous and/or concurrent treatment with other anti-cancer therapies is permitted. Patients who have previously received sipuleucel-t, meet study eligibility, and are not on the treatments listed above, are not considered on treatment. Patients

receiving experimental treatment with non-approved drugs at the time of enrolment are not eligible. Patients receiving treatment with combinations of approved drugs are eligible, provided documentation and clearance by the SCC.

Allocation within strata will be carried out using blocked randomisation in random blocks of 2, 4, or 6.

4.6 Blinding

Due to the nature of the intervention being tested (exercise), investigators, research staff and patients cannot be blinded to the patients' randomisation assignment. However, the laboratory processing patient samples and the statistician performing the *a priori* specified primary and secondary analyses will be blinded.

5.0 CLINICAL PROCEDURES

Guidelines for Pre-Study Testing:

All laboratory tests that are specified in the eligibility criteria (absolute neutrophil count, platelet count, creatinine, bilirubin, aspartate aminotransferase, PSA, serum testosterone) as well as blood-based markers that are part of the Halabi score should be completed within 28 days before Cycle 0, Day 1 (see footnote #7). The CPET must be completed within 14 days of Cycle 0, Day 1. Participants are randomised after the CPET.

Table 1. Summary of assessments. One cycle = 28 days. (Next page)

Table 1 Summary of Assessments	Screening	On-Treatment Study Period ¹																								Off-Treatment		
		Cycle 0: Baseline ²	Supervised Exercise								Transition			Self-managed exercise program														Follow-up Period
		0	1	2	3	4	5	6	7	8	9	10	11	12	13	14	15	16	17	18	19	20	21	22	23	24		
Informed Consent	X																											
Randomisation	X ⁴																											
Clinical History																												
Medical history ^{&}	X																										X	
Tumour histology	X																											
Medication/Tx history	X				X			X			X			X			X			X			X			X		
Body Measurements																												
Height	X ³																											
Weight, waist, hip circumference	X ³							X ⁵						X ⁵					X ⁵							X ⁵		
Lab Studies																												
CBC w/diff, blood chemistries ⁶	X ⁷				X ⁶			X						X ^{6,8}			X ⁶			X ^{6,8}			X ⁶			X ^{6,8}		
Fasting Lipid Profile (LDL, HDL, Triglycerides), fasting Glucose, HbA1c		X						X																				
Efficacy																												
Overall survival status, Disease progression, Symptomatic-skeletal event ⁹								X ⁹						X ⁹					X ⁹						X ⁹		Twice yearly ⁹	
WHO analgesic scale	X				X			X			X			X			X			X			X			X	Once yearly ⁹	
CPET with ECG ³	X ¹⁰							X ¹¹						X ¹¹														
ARM A - Constant Load test ¹⁰		X ¹⁰	X	X	X	X	X	X	X	X	X	X	X	X	X	X	X	X	X	X	X	X	X	X	X	X	X	
ARM A - 1-RM Strength test		X ¹⁰						X ¹¹			X ¹¹			X ¹¹					X ¹¹						X ¹¹			
ARM B - 1-RM Strength test		X ¹⁰						X ¹¹						X ¹¹					X ¹¹						X ¹¹			
400 m walk test		X ¹⁰						X ¹¹						X ¹¹					X ¹¹						X ¹¹			
Safety																												
Medical Clearance(s) ¹²	X							X						X					X									
Vital signs ¹³	X ³	X						X						X					X							X		
ECOG performance status	X				X			X			X			X			X			X			X			X		
Bone pain at exercise visits			Assessed at each supervised exercise visit using VAS																									
Adverse events ¹⁴	X ³		X	X	X	X	X	X	X	X	X	X	X	X	X	X	X	X	X	X	X	X	X	X	X	X	X	
Concomitant medications ¹⁵	X ³		X	X	X	X	X	X	X	X	X	X	X	X	X	X	X	X	X	X	X	X	X	X	X	X	X	

Table 1 Summary of Assessments (Continued)	Screening	On-Treatment Study Period ¹																								Off-Treatment	
		Cycle 0: Baseline ²	Supervised Exercise								Transition			Self-managed exercise program													
		0	1	2	3	4	5	6	7	8	9	10	11	12	13	14	15	16	17	18	19	20	21	22	23	24	
Metabolic Research Studies																											
Research blood (fasting)		X ¹⁶					X ¹⁷						X ¹⁷														X ¹⁷
FFPE tumour specimens		Request ¹⁸																									
Urine specimens		X					X						X														X
Patient Report Outcomes																											
Appx 5 Demographics & Health History Questionnaire		X ¹⁹																									
Appx 8 Exercise Screening Questionnaire		X																									X ²¹
FACT-G, EPIC-26, FACIT-Fatigue, EORTC QLQ-C30, STAI, CES-D, PSQI, falls ²⁰		X ¹⁹			X			X			X			X			X			X				X			X ²¹
BPI-SF and EQ5D ²⁰		X ¹⁹						X						X					X							X	X ²¹
Exercise questions modified from baseline, Modified Godin exercise scale, memory, exercise motivation ²⁰		X ¹⁹						X						X					X							X	
Diet ²⁰		X ¹⁹												X												X	
Cost of Participation								X						X													

TABLE ABBREVIATIONS:

EMR: electronic medical record; CPET: Cardiopulmonary Exercise Test; ECG: Electrocardiogram; SOC: Standard of Care; ECOG: Eastern Cooperative Oncology Group; PSA: Prostate Specific Antigen; EG: Exercise Group; FFPE: formalin-fixed paraffin-embedded; PFS: Progression-free survival; OS: overall survival; SSE: symptomatic skeletal-related events; BPI-SF: Brief-Pain Inventory Short Form; FACT-G: Functional Assessment of Cancer Therapy-General; FACIT: Functional Assessment of Chronic Illness Therapy; EPIC-26: Expanded Prostate Cancer Index Composite Instrument, EQ5D: Euro-Quality of Life 5-dimension; STAI: State-Trait Anxiety Inventory; CES-D: Centre for Epidemiologic Studies Depression

FOOTNOTES:

¹ The study period is comprised of cycles. Each cycle equals 28 days.

² Day 1 of the study period (baseline) is the same for each arm. It is defined as Day 1, Cycle 0 when the remainder of the baseline physical capacity and function tests are completed. Men are randomised prior to this day. This day is also the first day of training in the Supervised Exercise/SE (intervention arm). The patient is to be told which arm they are randomised into **after** Baseline testing is completed, which is at the end of Day 1, Cycle 0 testing – where “next steps” in the study are explained.

³ Assessed at screening visit with exercise physiologist, trainer, etc., which must occur within 14 days prior to Day 1, Cycle 0. Concomitant medications are recorded by clinical research coordinator in REDCap and exercise physiologist/trainer will review with patient at the CPET screening visit. The baseline anthropometric measurements do not need to be

re-assessed if these measurements were already taken within the same week (prior 6 days).

⁴Patients are randomised after successfully completing the CPET and prior to Day 1, Cycle 0. Current treatments must be submitted to ensure correct stratification.

⁵Follow-up measurements will be assessed by the exercise physiologist, trainer, etc.

⁶Includes: CBC with differential, total bilirubin, ALT, AST, ALP, Albumin, Sodium, Potassium, serum Calcium, Magnesium, BUN, Creatinine, Glucose, LDH, PSA, Testosterone, haemoglobin. All required at Cycle 6 only. Quarterly assessment can be obtained via SOC, For SOC, record the first instance of blood assessments obtained as SOC for each patient after Day 1 of the quarterly Cycles: 3, 9, 12, 15, 18, 21, and 24. If no SOC labs are ordered within the quarter, please indicate on blood assessments database form. (SOC Example: Patient starts Cycle 9, CBC w/ diff ordered for pt at Cycle 10, record values under Cycle 9 eCRF. If the CBC with diff is ordered again in the same quarter (e.g. Cycle 11), there is no need to record)

⁷All laboratory tests that are specified in the eligibility criteria (haemoglobin, ANC, platelet count, creatinine, bilirubin, AST, PSA, serum testosterone) and blood-based markers which are part of the Halabi score (PSA, LDH, albumin, ALP) should be completed within 28 days before Day 1, Cycle 0. Non-screening labs can be done at Cycle 0, with research bloods (participants are randomised after the CPET). For treatment naïve or stable (Groups 1 and 2): prefer 28 days or less, but will allow up to 42 days indicated as a deviation. For patients with PSA progression on abiraterone/enzalutamide or patients treated with docetaxel as first line therapy for mCRPC (Groups 3 and 4 and 5): must be completed within 28 days or less.

⁸The Halabi variables (PSA, LDH, albumin, haemoglobin, and ALP) are required at Cycles 12, 18, and 24. If site will incur a cost to order these assessments at Cycles 18 and 24, please record the values for these variables from the closest date to these time-points ordered as SOC. (SOC see footnote #6)

⁹Per review of medical records or other documentation by research assistant followed by confirmation by site PI. Mortality data will be collected through medical records, death records, and other resources every 6 months during the on-treatment and follow-up periods. If the participant is lost to follow-up, we will contact next of kin or alternate contact. Death certificates will be requested along with access to the medical records related to the death, and centrally reviewed to determine cause of death.

¹⁰The CPET is assessed prior to and within 14 days of Day 1, Cycle 0. *The CPET should only be performed after all other screening procedures are completed and verified as eligible.* The remainder of the physical function and strength tests (i.e., one repetition maximum chest press, leg press and seated row) will be carried out either on the day of the CPET or at Day 1, Cycle 0 (see protocol). Constant Load tests during follow-up will occur within 7 days *on or after* Day 1 of the Cycle.

¹¹Exercise assessments will occur within 7 days *on or after* Day 1 of the Cycle.

¹²Medical clearance(s) for continued participation must be documented by the treating physician every 6 months (SOM: [Appendix 9](#)) in the absence of any SAEs. (See “Safety Assessments on page 4)

¹³Blood pressure and heart rate are also assessed at the start of every session for patients in the SE (intervention) arm who are known to have high blood pressure, history of unstable blood pressure, symptomatic, or reports new treatment. If 2/3 readings demonstrate the pressure to be >160 OR >90 at the time of the session, exercise will be held on that day.

¹⁴Continuously reported from informed consent until 28 days after Cycle 24, Day 1. All adverse events (AE) should be followed to their resolution, until the PIs assess them as stable, irreversible, or until the patient refuses further follow up, whichever comes first. AEs are assessed by the exercise physiologist, trainer, etc. at on-site exercise visits and in all subjects (in person or by phone) on a monthly basis. AE events will be recorded on the AE form and logged in REDCap. AE assessment will include bone pain.

¹⁵Medications will be reviewed with the patient once a month, either in person or by phone call. Medications will be logged and entered into the REDCap database.

¹⁶Sec 8.3: Baseline blood collection will occur after the patient passes the baseline CPET, and will occur before or on Day 1, Cycle 0, before the remainder of the exercise tests are performed and at least 48 hours after any vigorous activity including the screening CPET visit

¹⁷Sec 8.3: Follow-up blood collection will occur prior to completing the exercise tests on that day (see footnote #11), and at least 48 hours after any vigorous activity. If it cannot be completed on that day, it must be completed within 7 days after Day 1 of the Cycle, at least 48 hours after any vigorous activity.

¹⁸Request access to available archival formalin-fixed paraffin-embedded (FFPE) tumour blocks or tumour slides from consenting patients for future biomarker analyses.

¹⁹The baseline surveys or FFQ will be completed within 28 days prior to the screening CPET and used as the baseline assessments

²⁰[Appendix 6, 20-27, 29, 31, 33](#). All follow-up surveys and FFQ will be completed within 7 days before the exercise assessment, except for [Appendix 20, 24, and 33](#), which are completed on paper at the visit or by mail.

²¹Selected assessments will be administered during the follow-up period on a yearly basis. If no response is received from the participant and medical records do not indicate death, we will follow up with the next of kin or alternate contact.

⁸New conditions diagnosed on-study are recorded during the on-study period.

Other Time restrictions not mentioned in the footnotes:

*A minimum of 48 hours recovery will be implemented between resistance training or HIIT of the same muscle group using a split program design.

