5.5.2.8 Complete Constant Load Exercise Test (intervention arm)

5.5.3 Within 7 days on or after Day 1 of Cycles 6, 12, 24 – ARMS A & B

Study Blood Draw Visit

5.5.3.1 Collect research fasting blood (cycles 6, 12, 24) and urine (cycles 6, 12, 24)

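### Baseline walk and 1RM tests follow randomisation with no stated masking of the tester, so an arm-related shift in change from baseline cannot be excluded

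*Combined protocol and SAP*

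**What the plan says.** - **Order.** Section 5.0, Table 1 footnote 4 and Section 5.5.1.8.5 put randomisation after the screening CPET. Footnote 2 describes Day 1, Cycle 0 as the day "when the remainder of the baseline physical capacity and function tests are completed" and adds "Men are randomised prior to this day". Section 5.2 sets the walk and strength tests at Cycle 0, and Section 5.5.2 lists them at the Day 1 visit (items 5.5.2.6 and 5.5.2.7).
- **Patient.** Footnote 2: "The patient is to be told which arm they are randomised into" only once baseline testing has finished.
- **Staff.** Section 4.6: "investigators, research staff and patients cannot be blinded". Only the laboratory and the analysing statistician are masked. Section 4.4 has the database randomise while "maintaining concealment from patients and recruiting staff"; testers are not mentioned.
- **Same-day use of the arm.** Item 5.5.2.8 is a constant load test for the intervention arm only, and footnote 2 makes this day the first training day in that arm.
- **Timing footnotes.** Footnote 10 says the remaining tests "will be carried out either on the day of the CPET or at Day 1, Cycle 0". Footnote 16 places the baseline blood draw "before the remainder of the exercise tests are performed and at least 48 hours after any vigorous activity including the screening CPET visit".
- **Use of the data.** Section 12.12, Analysis 1, takes the between-arm difference in change in leg extension and the 400 m walk after six months in the first 130 patients. A difference under 2.06 kg or under 3.5 s leads to considering protocol modifications. Section 12.9 compares physical function between arms at months 0, 6, 12, 18 and 24 and models change over time.

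**The concern.** The walk is done at the fastest pace the patient can manage, and a 1RM is the heaviest load he can lift once. Both respond to encouragement. Section 5.2.3 also gives the physiologist running the test a say in whether each 1RM is attempted, so even which baselines are missing could depend on arm. If the tester knows the allocation, the baseline stops being a pre-allocation measurement. Any difference that the tester introduces is then counted as part of the intervention's effect on change. At stake are Interim Analysis 1, which the protocol calls a futility analysis, and the change analyses of the walk and 1RM in Section 12.9.

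**Working it through.** **1. Sequence.** Screening CPET, then randomisation, then Day 1, Cycle 0: blood, walk, 1RM, and (Arm A) constant load test and first training. The walk and 1RM baselines follow randomisation.

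**2. Who is masked.** Patient: yes, until testing ends. Recruiting staff: allocation is concealed. Tester: no statement. Exercise staff need the arm before the visit is over.

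**3. Does footnote 10 give a pre-randomisation route?** Not a usable one. It allows the CPET day, but footnote 16 wants blood before the remaining tests and at least 48 hours after the CPET, so both cannot be met. Sections 5.2 and 5.5.2 also set the tests at Cycle 0. The strength tests that footnote 10 names are chest press, leg press and seated row. It names neither the walk nor leg extension, the two Interim 1 measures.

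**4. The plan's own figures (Section 12.12).** Threshold = effect size × SD of change.
- Walk: 0.40 × 8.75 = 3.50 s.
- Leg extension: 0.40 × 5.16 = 2.064 kg.
- Sample: 0.15 × 866 = 129.9, i.e. 130.

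All three reproduce.

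**5. How a shift passes through.** The difference in change is (follow-up A − baseline A) − (follow-up B − baseline B). If tester behaviour moves the Arm A baseline mean by δ relative to Arm B, this difference moves by exactly −δ.

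**6. Sensitivity of Interim 1.** Assumptions: 65 per arm, normal means, a true effect of 0.40 SD, and the same shift in SD units on both measures. The shift sizes and the correlation between measures are mine. SE = SD × √(2/65): 1.53 s for the walk and 0.91 kg for leg extension. P(one measure below threshold) = Φ(−shift / √(2/65)), with the shift in SD units and positive when it favours exercise. The last column is the either/or rule by bivariate normal, at correlation 0.5 and 0.

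| Shift (SD) | Walk (s) | Leg ext. (kg) | One measure below | Either below, r = 0.5 / 0 |
|---|---|---|---|---|
| +0.2 | 1.75 | 1.03 | 13% | 21% / 24% |
| +0.1 | 0.88 | 0.52 | 28% | 42% / 49% |
| 0 | 0 | 0 | 50% | 67% / 75% |
| −0.1 | −0.88 | −0.52 | 72% | 86% / 92% |
| −0.2 | −1.75 | −1.03 | 87% | 95% / 98% |

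Because the thresholds are 0.40 SD, shifts of 0.1 and 0.2 SD are 25% and 50% of them.

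**7. Tests of change with no true effect.** With d = shift / √(2/n), a nominal two-sided 5% test rejects with probability 1 − Φ(1.96 − d) + Φ(−1.96 − d).
- 65 per arm: 8.8% (0.1 SD) and 20.7% (0.2 SD).
- 412 per arm: 30% and 82%. This is an upper bound, since 412 is the number evaluable for survival and fewer will complete function tests.

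**The case against.** The strongest reply is that the protocol never says the tester knows the arm at the moment of testing. Section 4.6 is a general statement about the whole trial, and test conduct is delegated to the Study Operations Manual, which may say more. That stands. A reader might infer that the baseline tests are run by staff who know the allocation; the documents make this likely but do not state it. What they support is that no masking of the tester is specified.

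Other replies also stand:
- **Patient unmasking.** It is tempting to argue that the Arm A constant load test reveals the arm during the visit. It is listed after the walk and the 1RM, and footnote 2 keeps the patient masked until testing ends. If both are followed, the route through the patient's knowledge of his arm is closed.
- **Direction.** One might assume weaker encouragement in Arm A, flattering exercise. Section 6.1.1 bases resistance prescriptions on the chest press, leg press and seated row 1RM, so a tester who knows the arm also has reason to obtain a full maximum there, which works the other way.
- **Scope.** Section 12.9 also covers CPET measures, whose baseline precedes randomisation (Section 5.2), and comparisons of levels at 6 to 24 months, which do not use the baseline. It names no adjustment for baseline, and its month-0 comparison might expose a large shift.
- **Consequence.** Interim 1 is advisory and its rule is offered as an example.
- **Follow-up.** Later tests are open-label for tester and patient, so encouragement can still differ by arm then.

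These replies narrow the point. None supplies a masked or pre-randomisation baseline for the walk and leg extension.

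**Conclusion.** The point holds in a limited form. By default the baseline walk and 1RM are measured after randomisation, the tester is not stated to be masked, and staff need the arm the same day. An arm-related shift in these baselines, in either direction, cannot be excluded, and it would enter change from baseline in full. At an assumed 0.1 to 0.2 SD it would move the chance of one measure missing its Interim 1 threshold from 50% to between 28% and 13% if it favoured exercise, or to between 72% and 87% if it went against. These figures rest on assumed shifts and show sensitivity; they are not evidence that a shift will occur. In the Section 12.9 models the full shift applies if month 0 is treated as an outcome; the section does not say how baseline enters.

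A reader might go further and conclude that physical function as a whole, or the trial's main result, is compromised. The documents do not support that: the CPET baseline, the later level comparisons and overall survival are untouched. This is a cheap improvement to secondary endpoints and one advisory interim analysis.

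**What to change.** 1. Change Table 1 footnotes 2 and 4 and Section 5.5.1.8.5 so that the study database randomises, or releases the allocation to any site staff, only after the baseline 400 m walk and all 1RM results are entered and locked. This can happen on Day 1, Cycle 0.
2. State that the Arm A constant load test and first training session follow release.
3. Reconcile footnote 10 (CPET-day option, with the walk and leg extension not named) with footnote 16 and Sections 5.2 and 5.5.2.
4. State in Section 12.12 whether Interim 1 compares change or Cycle 6 level, since a baseline shift drops out of a comparison of levels.

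**Cost.** A release condition in a database that already performs the randomisation, plus an explicit visit order; no extra staff, visits or tests. The downside is that sites must hold a first training slot before the arm is known, and with 1:1 allocation about half of those slots will not be used. The change does not address open-label testing at follow-up.
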